Official Title: The Effects of Electrical Muscle Stimulation Exercise on Upper, Lower Extremity and Core Strength in Sedentary Women

NCT Number: Pending

Date: October 7, 2025

Prepared by: [name] [name]

[name]

Institution: 19 Mayıs University

The Effect of Electrical Muscle Stimulation Exercise on Lower, Upper Extremity, and Core Strength in Sedentary Women

Participants

Our study was conducted with 27 sedentary women between the ages of 19-24. The optimal number of subjects to participate in the study was determined using the GPower 3.1.3 program. The results indicated that a total of 16 subjects would be an appropriate sample size for the study (effect size r : 0.87, lower and upper critical p : 0.53, true power: 0.92). Before the study, the subjects were informed in detail and included in the study by obtaining an "Informed Consent Form".

[figure not shown]

Figure 1. Flowchart

Study Design

This study was designed as a 2-arm parallel-group randomized controlled trial comparing

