the effects of submaximal EMS exercises. The study was approved by the Ondokuz Mayıs University Clinical Research Ethics Committee (approval number: 021/482) and was conducted as per the ethical principles stated in the Declaration of Helsinki. The inclusion criteria of the participants were determined as being between the ages of 19-24, being female, and volunteering. Exclusion criteria were those who had cardiovascular, neurological, or orthopedic disorders, were pregnant or were planning to become pregnant. Subjects made a total of 10 visits, including the familiarization session for the study. During the first visit, participants were informed about test protocols. Anthropometric measurements were then taken and trial measurements were made. In the pre-, mid (week 4), and post (week 8) test periods, all participants performed 3 visits at 24-hour intervals for a total of 9 visits according to the test protocols they selected from the practice cards specified for each period, and mid and post-tests were arranged so that they did not coincide with training days. Practice cards were as follows: 1- modified push-up (MPU), Handgrip strength (HS), single hop for distance (SH), Biering Sorensen (Bie-sor), 2- Bent arm hanging (BAH), triple hop for distance (TH), crossover triple hop for distance (CH), v-sit flexor (V-sit) and 3- deep squat (DS), medial side triple hop for distance (MSTH), sit-up. After completion of the pre-tests, participants were randomized into one of two exercise groups using computer-validated software (www.random.org) and divided into EMS (n=15) and Control (CON) (n=16) groups. Participants who did not participate in regular exercises and tests in both groups were excluded from the study and the study was completed with 12 participants for the EMS group and 15 participants for the CON group. All measurements and exercises were done at the same time of the day (12:00-16:00). The participants performed warm-up exercises before the tests. Both groups were asked not to make any changes in their usual physical activity behavior. Also, all participants were instructed to maintain their normal dietary intake before and during the study. The endpoint of the study was determined as the participant withdrawing consent to participate in the study, the experts deciding that it was not appropriate for the participant to continue in the study, and non-compliance with the study protocol.

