## **The Effect of Electrical Muscle Stimulation Exercise on Lower, Upper Extremity, and Core Strength in Sedentary Women**

### **Statistical Analysis**

SPSS 21.0 package program was used for data analysis. The normality assumption of the data was examined with the Kolmogorov-Smirnov test and it was determined that the variables were normally distributed ( $p>0.05$ ). One-way analysis of variance in repeated measures and Mixed Design Analysis of Variance in Repeated Measures were applied to the data. Sphericity was examined with Mauchly's Sphericity test. The Sphericity Assumed test was used for those with equal variances ( $p>0.05$ ). In cases where variances were not equal ( $p<0.05$ ), the epsilon value ( $\epsilon$ ) was examined and Greenhouse and Geisser tests were used when  $\epsilon<0.75$  and Huynh-Feldt tests were used when  $\epsilon>0.75$ . Bonferroni test was used to determine the intergroup differences. Data were presented as mean and standard deviation and evaluated at a significance level of  $p<0.05$ .

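### The SAP plans no EMS minus CON difference with a confidence interval, and the precision of the difference in change cannot be recovered from means and SDs

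*SAP*

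**What the plan says.** The protocol opens its Study Design section with "This study was designed as a 2-arm parallel-group randomized controlled trial comparing" submaximal EMS exercise, so the quantity of interest is EMS against CON. Testing takes place "In the pre-, mid (week 4), and post (week 8) test periods". Women were randomised to "EMS (n=15) and Control (CON) (n=16) groups", and "the study was completed with 12 participants for the EMS group and 15 participants for the CON group".

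On models, the SAP (Statistical Analysis) says "One-way analysis of variance in repeated measures and Mixed Design Analysis of Variance in Repeated Measures were applied to the data". On between-group comparisons it says "Bonferroni test was used to determine the intergroup differences". On output it says only "Data were presented as mean and standard deviation and evaluated at a significance level of" p<0.05.

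In the text available, neither document mentions a between-group difference as an output, a confidence interval, a standard error, an SD of change, or an effect-size measure for results.

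**The concern.** A two-arm trial with a baseline and two follow-up visits asks whether one arm changed more than the other. The planned output describes each arm separately and attaches a significance criterion. The SD of a score measures the spread between women at one visit. It does not measure how precisely the arms' changes have been compared, which depends on how strongly a woman's later score follows her first.

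This matters most when numbers are small. With 12 and 15 women, a result with p≥0.05 may mean that EMS does little, or that the trial could not tell. An interval for the difference shows which; a table of means and SDs with a p-value may not.

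**Working it through.** **The plan's own figure.** The documents give no figure for precision. The only planning figure is the protocol's total of 16 subjects (Participants), with "effect size r : 0.87, lower and upper critical p : 0.53, true power: 0.92". The test behind it is not stated. Read as a two-sided 5% correlation test at N = 16, the critical r is 0.497 and the power 0.998, so the set does not reproduce on that reading. That is a separate matter, and nothing below uses it.

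**Inputs.**
- Analysed numbers 12 and 15 (protocol, Study Design).
- Significance level 0.05 (SAP); two-sided is my assumption.
- The pre-post correlation r is not in the documents, so it is varied. Equal SDs over time and in both arms are assumed.
- The model is a two-sample t on one change score, without Bonferroni. It illustrates scale. It is not the planned three-visit mixed ANOVA, and 0.80 SD is not that analysis's threshold.

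**Step 1: significance threshold, in SD of change.** The half-width is t(0.975, 25) × √(1/12 + 1/15) = 2.06 × √0.15 = 2.06 × 0.387 = 0.798. An observed difference must reach about 0.80 SD of change.

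**Step 2: chance of missing a true effect, in SD of change.** Noncentral t with 25 df and noncentrality d × √(12 × 15 / 27) = 2.58d:
- d = 0.5: power 0.237, missed 76%
- d = 0.8: power 0.510, missed 49%
- d = 1.0: power 0.699, missed 30%

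**Step 3: precision in SD of the score.** The SD of change is √(2(1 − r)) score SD, so the half-width for the difference in change is 0.798 × √(2(1 − r)). For a baseline-adjusted difference it is about t(0.975, 24) × √0.15 × √(1 − r²) = 2.064 × 0.387 × √(1 − r²), ignoring chance imbalance at baseline.

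| Assumed r | SD of change | Half-width, change | Half-width, baseline-adjusted |
|---|---|---|---|
| 0.3 | 1.183 | 0.94 | 0.76 |
| 0.5 | 1.000 | 0.80 | 0.69 |
| 0.7 | 0.775 | 0.62 | 0.57 |
| 0.8 | 0.632 | 0.50 | 0.48 |
| 0.9 | 0.447 | 0.36 | 0.35 |
| 0.95 | 0.316 | 0.25 | 0.25 |

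Every row is compatible with the same table of means and SDs. The crude week-8 interval that a reader could build has a half-width of 0.80 score SD whatever r is. If r were 0.9, that would be 0.80 / 0.35 = 2.3 times the width of the baseline-adjusted interval.

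**Step 4: why the two units must be kept apart.** A true effect of 0.5 score SD is 0.5 SD of change at r = 0.5 (power 24%). At r = 0.9 it is 0.5 / 0.447 = 1.12 SD of change (power 79%). The 76% in Step 2 therefore applies to 0.5 SD of change, not to 0.5 SD of the score.

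**The case against.** The strongest reply is that much of what is wanted is already there. Arm means at three visits give the EMS minus CON difference in change by subtraction. Means, SDs and n give a crude week-8 interval. A mixed-design ANOVA and a Bonferroni comparison between groups are planned. This stands, and it rules out the stronger reading that no effect can be found in the output or that a non-significant result is beyond interpretation. What is lost is the precision of the difference in change.

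The SAP also does not say that F statistics or exact p-values will be withheld. That is fair: printed statistics for suitable contrasts could allow the SD of change to be worked back. But the SAP promises none, and the F for group by time over three visits has 2 numerator df, so it does not convert directly into a standard error for the week-8 difference.

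A reader might further infer that most outcomes will be non-significant even if EMS works. The figures support this only for true effects below about 0.8 SD of change: power is 51% at 0.8 and 70% at 1.0. The documents give no expected effect in those units. Nor do they say that p≥0.05 will be described as no effect. They contain no outcome results, so the point concerns what is planned.

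Finally, low power is a separate issue. An interval displays imprecision and does not cure it.

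**Conclusion.** The point holds as a gap in planned reporting. The SAP does not plan an EMS minus CON difference with its precision, and means and SDs alone do not yield the precision of the difference in change. The planned tests are not invalidated.

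The size rests on an assumed correlation. From 0.3 to 0.95 the half-width for the difference in change varies almost fourfold (0.94 / 0.25 = 3.8). These are illustrative values, and a reader should not take them as bounds. The threshold of about 0.80 and the 76% miss rate are in SD of change and belong to the simple t comparison. The conclusion does not depend on any one value: at 12 v 15, p≥0.05 by itself does not distinguish no effect from too little precision.

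**What to change.** Replace the SAP's presentation sentence with wording such as: *For each quantitatively scored test, the baseline-adjusted EMS minus CON difference at week 4 and at week 8 will be reported in the test's own units with its 95% confidence interval, together with the mean and SD of change in each arm. Conclusions will be based on the interval, and p≥0.05 will not be described as no effect.*

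The restriction to quantitatively scored tests is needed because the protocol's Deep Squat Test section gives no score or unit. Baseline adjustment is preferred to the raw change score because it is usually more precise (0.69 v 0.80 score SD at an assumed r of 0.5).

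The cost is SAP wording and one extra table. The protocol describes the testing as done, so no new data are needed; the change should be recorded as made after data collection. The downside is small: the practice cards list 11 tests, so two time points give up to 11 × 2 = 22 intervals (20 if the deep squat is left out), taking one score per test. The table should state that they are not adjusted for multiplicity.
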